6.0 HUMAN SUBJECTS PROTECTIONS

6.1 RATIONALE FOR SUBJECT SELECTION

This is a study for patients with prostate cancer. The patient population in whom this disease occurs is older adult males. This disease does not occur in children; therefore, children will not be part of this study. All ethnic groups/ race categories would be represented as they are represented in the disease as a whole. Decisionally impaired individuals will not be included in this study, if they are unable to sign informed consent. Physically impaired persons who otherwise satisfy eligibility criteria will be included in this study.

6.2 PARTICIPATION OF CHILDREN

Adenocarcinoma of the prostate is not a disease of children, therefore, children will not be considered as research subjects for this study.

6.3 EVALUATION OF BENEFITS AND RISKS/DISCOMFORTS

The medical risks associated with this study are those normally expected risks associated with external beam radiotherapy and high dose rate brachytherapy for prostate cancer. Common acute and temporary side effects include fatigue, urethritis, cystitis and proctitis. Uncommon long-term side effects may include urinary frequency, urgency, incontinence, rectal bleeding, perineal pain, tenesmus, erectile dysfunction, bowel adhesions causing obstruction and infertility. Very rare long-term complications may include lymphedema, pathologic femoral neck fractures, and a second primary malignancy.

Patients on this study will be receiving treatment for their prostate cancer. Other potential benefits of participation may include fewer side effects of radiation treatment due to a better visualization of the anatomy and sparing of normal structures. The information learned from this study may also benefit other patients with prostate cancer in the future.

6.4 CONSENT AND ASSENT PROCESSES AND DOCUMENTS

The Principal Investigator and associates will recruit patients. The investigational nature and objectives of this study, the procedures involved and their attendant risks and discomforts, will

be carefully explained to the patient, and a signed informed consent document will be obtained. It is our goal to be as explicit as possible in verbal and written consent procedures to insure that all participants are joining the study without coercion.

Patients who meet study eligibility criteria, and who are willing to participate in the study, will be consented by the PI or associates. The consent form will be discussed with the patient in person. Informed consent will involve careful explanation of all items outlined in the consent form. This discussion includes the investigational nature of this study, and the possibility of lack of direct benefit to the research subject. All information will be reported in summary fashion only. A separate anesthetic/operative consent will be obtained at the time of the procedure

6.5 PATIENT ADVOCATE

The patient's rights representative is available to patients on this protocol at [contact] in [name], NIH. Patients may ask any questions about the study and may withdraw their consent at any time without compromising their medical care.

7.0 DATA REPORTING

7.1 PATIENT REGISTRATION FORM

Demographic information and results of pretreatment studies should be entered and reported to Harris Technical Information Services at the time of patient entry onto the trial (see section 2.3).

7.2 DATA SUBMISSION

- Summary information will be submitted to the IRB annually for continuing review and at the completion of the study.
- Data may be reported in laboratory publications as derived from pilot studies. Patients will not be indicated by name.

7.3 DEFINITIONS

7.3.1 *Adverse Events*

An adverse event is defined as any reaction, side effect, or untoward event that occurs during the course of the clinical trial associated with the use of a drug in humans, whether or not the event is considered related to the treatment or clinically significant. For this study, AEs will include events reported by the patient, as well as clinically significant abnormal findings on physical examination or laboratory evaluation. A new illness, symptom, sign or clinically significant laboratory abnormality or worsening of a pre-existing condition or abnormality is considered an AE. All AEs must be recorded on the AE case report form unless otherwise noted above in Section 5.1.

All AEs, including clinically significant abnormal findings on laboratory evaluations, regardless of severity, will be followed until satisfactory resolution. AEs should be reported up to 30 days following the last dose of study drug.

An abnormal laboratory value will be considered an AE if the laboratory abnormality is characterized by any of the following:

- Results in discontinuation from the study
- Is associated with clinical signs or symptoms
- Requires treatment or any other therapeutic intervention
- Is associated with death or another serious adverse event, including hospitalization.
- Is judged by the Investigator to be of significant clinical impact
- If any abnormal laboratory result is considered clinically significant, the investigator will provide details about the action taken with respect to the test drug and about the patient's outcome.

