- The prostate will be treated to 7560 cGy in 180 cGy daily fractions (42 fractions.)
 - The maximum dose 7 mm or more beyond the prostate will be no more than 7560 cGy.
 - No More than 25% percent of the rectal volume shall receive more than 70 Gy.
 - The maximum dose to the prostatic urethra, bladder, and rectum will be limited to 78 Gy.
- For the first 25 fractions, in addition to the prostate, the high risk lymph node bearing regions of the pelvis will also be treated with IMRT to a total dose of 4500 cGy.
- The maximum dose 7 mm beyond the lymph node regions will be no more than 5040 cGy.
 - No more than 10cc of the small bowel will receive more than 55 Gy.
- There will be daily localization of the prostate and fiducial markers using portal imaging.
- All patients will receive 5 further CT simulation studies during the course of therapy
 - We will again run the initial plan on these subsequent CT simulations.
 - We will compare the dosimetry parameters above across the CT simulations
 - This analysis will allow us to determine what margins are truly appropriate to provide adequate coverage of the target volumes
- All patients will receive neoadjuvant, concurrent, and adjuvant hormone therapy.

Treatment

After the First 10 Patients (Phase I Dose Escalation)

- The MRI of the prostate and pelvis will be registered to the treatment planning CT scan.
- The prostate will be treated to 7560 cGy in 180 cGy daily fractions (42 fractions.)
- The maximum dose 7 mm or more beyond the prostate will be no more than 100% of the prescription dose of 7560 cGy.
 - No More than 25% percent of the rectal volume shall receive more than 70 Gy.
 - The maximum dose to the urethra, rectum and bladder will be limited to 78 Gy.
- In addition to the prostate, the high risk lymph node bearing regions of the pelvis will also be treated with IMRT in 180 cGy daily fractions. Total dose will be determined by dose cohort.
- The maximum dose 7 mm beyond the lymph node regions will be no more than 5040 cGy.
 - No more than 10cc of the small bowel will receive more than 55 Gy.
- There will be daily localization of the prostate and fiducial markers using portal imaging.
- All patients will receive neoadjuvant, concurrent, and adjuvant hormone therapy.

Follow Up:

- Toxicity
- MRI to evaluate for changes in imaging.
- Genomic and proteomic study of biopsied tissue

Table of Contents

1. Introduction	
1.1 Study Objectives.....	5
1.2 Background and Rationale.....	5

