3.1.4 Definition of Dose Limiting Toxicity (DLT)

An acute DLT will be defined as RTOG grade 3 or greater, acute GI or GU toxicity (see appendix IIA) within 3 months after the completion of radiation. Thus, accrual to an escalated dose cohort may need to be delayed so that all 3 patients in the current cohort are followed for 2 months. Given that the volume of normal tissue irradiated to standard dose or higher will be substantially limited, late toxicity is less of a concern than acute toxicity.

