3.4.4 Post Active Treatment Evaluation (follow- up)

- Upon completion of therapy, patients will be evaluated at 2, 4, 8 and 12 weeks for acute effects of radiation therapy. Patients will be evaluated at 6, 9, 12, 18 and every 6 months afterward for late effects until 36 months.
- Follow-up visits will include:
 - A directed history and physical examination,
 - PSA evaluation
 - Rectal toxicity assessment including:
 - RTOG acute toxicity grading- GI & GU (Appendix IIA)
 - RTOG Late toxicity grading- GI & GU (Appendix IIB)
 - EPIC (Appendix IIIC).
 - AUA Symptom Score (Appendix IV)
 - Sexual Health Inventory For Men (Appendix V)
- Follow-up MRI may be obtained after completion of therapy to better delineate the time of course of signal change after radiation therapy.

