3.7 RADIATION THERAPY GUIDELINES

Radiation Therapy is part of the primary protocol treatment and is therefore included in section 3.2.3

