7.4.2 NCI-IRB Requirements for PI Reporting at Continuing Review

The protocol PI will report to the NCI-IRB:

1. A summary of all protocol deviations in a tabular format to include the date the deviation occurred, a brief description of the deviation and any corrective action.
2. A summary of any instances of non-compliance
3. A tabular summary of the following adverse events:
 - All Grade 2 **unexpected** events that are possibly, probably or definitely related to the research;
 - All Grade 3 and 4 events that are possibly, probably or definitely related to the research;
 - All Grade 5 events regardless of attribution;
 - All Serious Events regardless of attribution.

NOTE: Grade 1 events are not required to be reported.

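### Section 7.3.1 ties adverse-event reporting to an undefined study drug in a radiation trial; counted from the last fraction, it ends with two thirds of the post-radiation DLT window and every late-effects visit still to come.

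*Combined protocol and SAP*

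**What the plan says.** Section 7.3.1 describes an adverse event as one "associated with the use of a drug in humans" and sets the reporting limit: "AEs should be reported up to 30 days following the last dose of study drug". The same section requires every adverse event to go on the case report form, and says that adverse events of any severity "will be followed until satisfactory resolution".

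Other sections describe a trial with a different intervention and longer clocks:

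- **Treatment.** Section 3.7: "Radiation Therapy is part of the primary protocol treatment". Section 8 lists only an antibiotic, a local anesthetic, an MRI contrast agent and an enema. The schema adds "All patients will receive neoadjuvant, concurrent, and adjuvant hormone therapy", and section 3.5 treats this as concurrent therapy. None of these is called the study drug.
- **DLT.** Section 3.1.4 counts grade 3 or greater "acute GI or GU toxicity (see appendix IIA) within 3 months after the completion of radiation".
- **Follow-up.** Section 3.4.4 has acute visits at weeks 2, 4, 8 and 12 after therapy. It continues: "Patients will be evaluated at 6, 9, 12, 18 and every 6 months afterward for late effects until 36 months".
- **IRB reporting.** The continuing-review table in 7.4.2 includes "All Grade 3 and 4 events that are possibly, probably or definitely related to the research", together with all serious events whatever their cause. Neither 7.4.1 nor 7.4.2 gives a 30-day limit.

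**The concern.** The reporting clock starts from an event that this trial does not define. Staff at the site could choose different start points and each defend the choice. On the reading closest to the trial's treatment, the last fraction, the clock stops before the protocol's own DLT window closes and before late follow-up begins.

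The secondary objective in section 1.1 is long-term effects and toxicity, and section 5.4 plans to tabulate late toxicities. Section 6.3 names lymphedema, femoral neck fracture and second malignancy among the long-term complications. If reporting lapses at day 30, these depend on a clinician noting them at a visit, with no explicit rule that carries them into a report. Section 7.5.1 describes monitoring by the research team only, so the IRB table is the one outside view of such events that these sections provide. Higher dose cohorts may be opening while patients in earlier cohorts reach their late visits.

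**Working it through.** **1. The plan's own figure.** Section 5.4 gives escalation probabilities of 0.91, 0.49, 0.17 and 0.03 at DLT probabilities p of 0.1, 0.3, 0.5 and 0.7. Under the rule in 3.1.3, P(escalate) = (1−p)³ + 3p(1−p)² × (1−p)³.

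- p = 0.1: 0.729 + 0.243 × 0.729 = 0.906
- p = 0.3: 0.343 + 0.441 × 0.343 = 0.494
- p = 0.5: 0.125 + 0.375 × 0.125 = 0.172
- p = 0.7: 0.027 + 0.189 × 0.027 = 0.032

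All four reproduce. They depend on the DLT definition in 3.1.4, not on the adverse-event clock in 7.3.1.

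**2. Possible anchors for the 30 days.**

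- *A section 8 agent.* These serve the biopsy and MRI. If the last one is given around the biopsy, the period can end before radiation does, since 42 weekday fractions take about 42/5 = 8.4 weeks. An optional contrast MRI after therapy (3.4.4) could reopen it.
- *Hormone therapy.* Section 1.2.3 calls for at least 3 years or indefinite treatment, and 3.5 allows indefinite adjuvant treatment in higher-risk patients. The period could outlast the 36-month follow-up.
- *The last fraction.* This is quantified next.

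**3. Coverage of the DLT window, counted from the last fraction.** Take 3 months as about 91 days.

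- Covered: 30/91 = 33%. Outside: 61/91 = 67%.
- With a window of 84 to 92 days, 64% (54/84) to 67% (62/92) is outside.
- If the on-treatment weeks are added (56 to 58 days of radiation), the share outside falls to between 54/142 = 38% and 61/147 = 41%. So the two-thirds figure applies only to the post-radiation window.

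**4. Coverage of visits (3.4.4).** The acute visits fall on days 14, 28, 56 and 84, so 2 of 4 are within 30 days. The late visits are at months 6, 9, 12, 18, 24, 30 and 36, so 0 of 7 are. In total, 2 of 11.

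**5. What still captures an event after day 30.**

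- *GI/GU toxicity, acute or late:* scheduled RTOG grading to month 36 (3.4.4), toxicity assessment in the database (5.1), tabulation (5.4).
- *Deaths not due to progression, and unanticipated problems:* 7.4.1, with no time limit stated.
- *Related grade 3–4 and serious events:* listed in 7.4.2 with no time limit stated. However, that list is a summary of adverse events, the term that 7.3.1 defines and limits, and the definition of serious in 7.3.5 rests on the same term.
- *Late events off the GI/GU scales:* a directed history and examination takes place (3.4.4), and 7.3.1 requires adverse events to be recorded, but its reporting sentence has lapsed. Section 5.3 adds CTC grading for acute toxicities only, without a visit schedule.

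**The case against.** The strongest reply is that this is template wording with little consequence. Much of that stands: 7.3.1 makes recording on the form mandatory without a time limit in that sentence, follow-up visits include history and examination, the research team reviews each patient's adverse-event data (7.5.1), and serious events enter the 7.4.2 table whatever the organ or cause.

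A reader might go further than the documents allow in four ways:

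- *That most of the DLT window and all late toxicity fall outside safety reporting.* RTOG GI/GU grading runs to 36 months, and 7.4.1 and 7.4.2 carry no 30-day limit.
- *That DLTs would be missed and escalation made too easy.* If DLTs were counted only from adverse-event reports and a third were captured, a true rate of 0.3 would act like 0.1, and the escalation probability would rise from 0.494 to 0.906. Nothing says DLTs are counted that way. Section 3.1.4 defines them by RTOG grade, and 7.5.1 bases escalation on toxicity data.
- *That the 7.4.2 table inherits the cut-off.* This is an inference from shared terminology. The text supports doubt, not a conclusion.
- *That coverage after radiation is nil, or that other events have no collection route.* The first rests on one choice of anchor and ignores a possible later contrast dose. The second ignores the visits and the recording rule.

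The reply does not supply an anchor. The follow-until-resolution rule concerns events already identified, and expedited reporting of an unanticipated problem requires that the event be unexpected, which a complication already listed in 6.3 will usually not be.

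**Conclusion.** The point holds as a defect in a stated rule. Section 7.3.1 defines adverse events by drug use and ends their reporting at a date that cannot be fixed from the protocol. On the last-fraction reading it covers 33% of the post-radiation DLT window, 2 of 11 follow-up visits and none of the late-effects visits.

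Two consequences follow. Reporting of later events off the GI/GU scales can lapse, despite the secondary objective on long-term toxicity. It is also unclear whether the 7.4.2 table covers grade 3–4 and serious events after day 30.

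The percentages assume that the clock starts at the last fraction and that 3 months is about 91 days. The examples from 6.3 are taken to lie off the scales from the scales' GI/GU titles. Section 6.3 calls these complications very rare and the trial enrols at most 19 patients, so few such events should be expected. The primary endpoint, DLT counting and the escalation probabilities are unaffected.

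**What to change.** In section 7.3.1:

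- Define adverse events by the study interventions: radiation, biopsy, marker placement and MRI contrast.
- Anchor the reporting period to the last radiation fraction, and run it at least to the end of the 3-month DLT window in 3.1.4.
- After that, report events of grade 3 or higher that may be related to the research, and all serious events, until the patient leaves the study (up to 36 months).

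In section 7.4.2, state that the table covers this whole period.

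The essential parts are a defined anchor, consistency with 3.1.4 and 3.4.4, and a stated reach for 7.4.2. The grade threshold for the later period is a proposal that keeps the workload low. The cost is a wording amendment and a few more adverse-event forms at visits that already take place. No sample size, escalation rule or probability changes.

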7.3.2 Suspected adverse reaction

Suspected adverse reaction means any adverse event for which there is a reasonable possibility that the drug caused the adverse event. For the purposes of IND safety reporting, 'reasonable possibility' means there is evidence to suggest a causal relationship between the drug and the adverse event. A suspected adverse reaction implies a lesser degree of certainty about causality than adverse reaction, which means any adverse event caused by a drug.

7.3.3. Unexpected adverse reaction

An adverse event or suspected adverse reaction is considered "unexpected" if it is not listed in the investigator brochure or is not listed at the specificity or severity that has been observed; or, if an investigator brochure is not required or available, is not consistent with the risk information described in the general investigational plan or elsewhere in the current application. "Unexpected" also refers to adverse events or suspected adverse reactions that are mentioned in the investigator brochure as occurring with a class of drugs or as anticipated from the pharmacological properties of the drug, but are not specifically mentioned as occurring with the particular drug under investigation.

7.3.4 Serious

An Unanticipated Problem or Protocol Deviation is serious if it meets the definition of a Serious Adverse Event or if it compromises the safety, welfare or rights of subjects or others.

7.3.5 Serious Adverse Event

An adverse event or suspected adverse reaction is considered serious if in the view of the investigator or the sponsor, it results in any of the following:

- Death,
- A life-threatening adverse drug experience
- Inpatient hospitalization or prolongation of existing hospitalization
- Persistent or significant incapacity or substantial disruption of the ability to conduct normal life functions

- A congenital anomaly/birth defect.
- Important medical events that may not result in death, be life-threatening, or require hospitalization may be considered a serious adverse drug experience when, based upon appropriate medical judgment, they may jeopardize the patient or subject and may require medical or surgical intervention to prevent one of the outcomes listed in this definition.

7.3.6 Disability

A substantial disruption of a person's ability to conduct normal life functions.

7.3.7 Life-threatening adverse drug experience

Any adverse event or suspected adverse reaction that places the patient or subject, in the view of the investigator or sponsor, at immediate risk of death from the reaction as it occurred, i.e., it does not include a reaction that had it occurred in a more severe form, might have caused death.

7.3.8 Protocol Deviation (NIH Definition)

Any change, divergence, or departure from the IRB-approved research protocol.

7.3.9 Non-compliance (NIH Definition)

The failure to comply with applicable NIH Human Research Protections Program (HRPP) policies, IRB requirements, or regulatory requirements for the protection of human research subjects.

7.3.10 Unanticipated Problem

Any incident, experience, or outcome that:

- Is unexpected in terms of nature, severity, or frequency in relation to
 - (a) the research risks that are described in the IRB-approved research protocol and informed consent document; Investigator's Brochure or other study documents, and
 - (b) the characteristics of the subject population being studied; **AND**
- Is related or possibly related to participation in the research; **AND**
- Suggests that the research places subjects or others at a *greater risk of harm* (including physical, psychological, economic, or social harm) than was previously known or recognized.

7.4 NCI-IRB AND CLINICAL DIRECTOR REPORTING

7.4.1 NCI-IRB and NCI CD Expedited Reporting of Unanticipated Problems and Deaths

The Protocol PI will report in the NIH Problem Form to the NCI-IRB and NCI Clinical Director:

- All deaths, except deaths due to progressive disease

- All Protocol Deviations
- All Unanticipated Problems
- All non-compliance

Reports must be received within 7 days of PI awareness via iRIS.

7.4.2 NCI-IRB Requirements for PI Reporting at Continuing Review

The protocol PI will report to the NCI-IRB:

1. A summary of all protocol deviations in a tabular format to include the date the deviation occurred, a brief description of the deviation and any corrective action.
2. A summary of any instances of non-compliance
3. A tabular summary of the following adverse events:
 - All Grade 2 **unexpected** events that are possibly, probably or definitely related to the research;
 - All Grade 3 and 4 events that are possibly, probably or definitely related to the research;
 - All Grade 5 events regardless of attribution;
 - All Serious Events regardless of attribution.

NOTE: Grade 1 events are not required to be reported.

7.5 DATA AND SAFETY MONITORING PLAN

7.5.1 Principal Investigator/Research Team

The clinical research team will meet on a regular basis weekly when patients are being actively treated on the trial to discuss each patient. Decisions about dose level enrollment and dose escalation if applicable will be made based on the toxicity data from prior patients.

All data will be collected in a timely manner and reviewed by the principal investigator or a lead associate investigator. Adverse events will be reported as required above. Any safety concerns, new information that might affect either the ethical and or scientific conduct of the trial, or protocol deviations will be immediately reported to the IRB using iRIS.

The principal investigator will review adverse event and response data on each patient to ensure safety and data accuracy. The principal investigator will personally conduct or supervise the investigation and provide appropriate delegation of responsibilities to other members of the research staff.

